PE Audit and Feedback Pilot Study
NCT05509803
1K01HL151805
Study Protocol and Statistical Analysis Plan
October 3, 2025

Study Protocol

The objective of this study is to determine a cost-effective and scalable tool to increase schools' compliance with state PE laws. Our recent survey of all elementary school principals in REDACTED DISTRICT identified 15 elementary schools that are currently non-compliant (or unsure about compliance) with the California state PE law. We will repeat this survey to obtain current data and from the pool of schools with the lowest reported weekly PE minutes. For both the recently completed survey and for the survey to be repeated, no human subjects data are included and the principals themselves are not human subjects as no information about the principals was/will be collected. From the ~15 elementary schools identified as non-compliant with state PE law, we will stratify schools by enrollment and proportion of low-income students enrolled (two key factors known to impeded PE law compliance) and use block randomization to randomize schools to intervention (n=5) and control (n=5) arms, ensuring equal representation across strata. If schools choose not to participate, then we will re-run randomization to also include the schools not initialize randomized to participation until we have achieved our sample of 10 schools that are willing to participate.

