REDACTED DISTRICT personnel will be trained to implement the PE audit and feedback tool in the fall of pilot year 1 (PY1) and will collect audit data in the spring. REDACTED DISTRICT will give feedback to school principals during one-on-one meetings in the fall of PY2. The intervention will take place over 2 years (PY2 and PY3). At the start of PY1-PY3, researchers will obtain school-level PE master schedules, which contain PE times for all classes in the school. Administrators at participating schools will either provide study team contact information to prospective 2nd and 5th grade teacher participants or will forward a recruitment email that the research team has written onto prospective participants so that prospective participants may make the first point of contact with our team if they are interested in participating. Our team will not be provided with names or contact information of prospective participants in order to recruit prospective participants. All recruitment materials and consent forms will emphasize the voluntary nature of participation in the research and that participants are free to skip/not answer any question that they do not wish to answer and are free to stop participating in the research at anytime. Once consented to participate, researchers will collect 2nd and 5th grade teachers' individual classroom PE schedules (we know PE operates differently in lower (Kindergarten – 2nd) and upper (3rd – 5th) elementary grades, which is why these two grades have been chosen.

During the fall and spring of PY1-PY3 we will collect objective data on PE class length and proportion of class spent in moderate to vigorous physical activity using the validated System for Observing Fitness Instruction Time (SOFIT) tool, observing 3 PE classes of 2 randomly selected 2nd and 5th grade teachers (n=4 teachers) and the PE teacher (if there is one) at each school on random days, per semester. Random day selection for observation days allows verification of self-reported PE minutes. SOFIT data will be collected by members of the research team who have been trained in the SOFIT protocol (and who have been CITI certified) and who have been fingerprinted and background checked and approved to visit REDACTED DISTRICT schools.

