The observer will arrive 15 minutes prior to the scheduled start of the PE class to situate him/herself. During observations investigators will have no interactions with teachers or students. Once the class has arrived at the PE area (i.e. gym or blacktop), the observer will randomly select four target students to observe during the lesson (2 girls and 2 boys). No individually identifiable information will be collected on students being observed. The observer will observe Student One for 4 minutes and then rotate to focus on the four students for four minutes each until the lesson ends. A pacing MP3 played through headphones will prompt the observer to collect data every 20 seconds on 1) the activity level of the student being observed (ranging from 1 (sedentary) to 5 (very active)) and 2) what type of activity the whole class is engaged in (game play, fitness, skill acquisition, knowledge acquisition, management, or other). The observer will begin the observation period when the teacher and 51% of the class has reached the instructional station and continue until half the class has departed from the area. The observer will also collect information at the class level, including on the length (in minutes) or the PE class, weather conditions if the class took place outside, class size (and number of boys and girls in the class), and whether the teacher was administering the state FitnessGram test during class. The only identifiable information that will be collected will be the teacher name (this enables the observer to make sure he/she is observing the correct PE class), the teacher type (2nd grade, 5th grade, or PE), and the teacher's sex (M/F).

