Teacher and/or student participation during the observation portion of Phase 2 requires no extra time commitment of participants outside of their normal PE class. Members of the research team will not be asking the schools/district to implement curriculum changes. Instead, we will be evaluating whether or not the tool provided feedback to the schools in a manner that allowed the schools to make the necessary changes in order to comply with state law. We will assess adoption, implementation, and maintenance of the PE audit and feedback tool through interviews with: district-level personnel involved in implementing the PE audit and feedback tool; principals in the 5 intervention schools; and all 2nd grade, 5th grade, and PE teachers observed in intervention schools. We will also conduct interviews with principals and teachers observed in the 5 control schools. These interviews will take place in PY2 and PY3 and will last approximately 20-30 minutes each. If a teacher or administrator participates in the study during both years, he/she will be interviewed twice (once in PY1 and once in PY2, after SOFIT observations are conducted in the spring). A semi-structured interview guide will enable the collection of data to assess RE-AIM components, including questions about: who teaches PE; priority for PE; the use of the PE audit and feedback tool; barriers encountered; successes and struggles with providing and sustaining mandated PE minutes; and plans for continuing to implement the PE audit and feedback tool and provide mandated minutes.

Statistical Analysis Plan

School-level demographic data will be downloaded from the California Department of Education's Data Quest website. Differences in school-level characteristics between all district elementary schools and study schools, as well as between intervention and control schools, will be determined using unpaired t-tests. Linear mixed effects models with random effects for school and grade will be used to determine 1) within-group changes and 2) difference in change between intervention and control schools in: scheduled minutes of physical education/week;

estimated minutes of physical education/week; and the proportion of observed lesson time in MVPA. All analyses will be performed using Stata/ SE (16.1).

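### The MVPA outcome is rated by research-team observers whom the plan does not keep unaware of arm, separate from interviewing, or balance across arms

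*Combined protocol and SAP*

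**What the plan says.** The allocation unit is the school: the Study Protocol will "use block randomization to randomize schools to intervention (n=5) and control (n=5) arms". SOFIT observations run in the fall and spring of PY1 to PY3, "observing 3 PE classes of 2 randomly selected 2nd and 5th grade teachers (n=4 teachers"), plus the PE teacher where a school has one.

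On who observes, the text says "SOFIT data will be collected by members of the research team who have been trained in the SOFIT protocol". On the children, "the observer will randomly select four target students to observe during the lesson (2 girls and 2 boys"). Every 20 seconds the observer records "the activity level of the student being observed (ranging from 1 (sedentary) to 5 (very active")) and the type of class activity. Observation starts once the teacher and 51% of the class are in place, and stops when half the class has left.

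Interviews in the intervention arm cover district staff, "principals in the 5 intervention schools; and all 2nd grade, 5th grade, and PE teachers observed in intervention schools". Principals and observed teachers in control schools are interviewed too. The interview guide asks how the audit and feedback tool was used.

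The Statistical Analysis Plan lists "the proportion of observed lesson time in MVPA" as one of three outcomes. It uses linear mixed models with random effects for school and grade to test the difference in change between arms.

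The documents do not mention masking of observers, separation of observers from those who randomize or interview, balance of observers over arms, observer identity, or the mechanism for the random pick of children.

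**The concern.** The Study Protocol calls the SOFIT data objective, but the MVPA share is built from a person's repeated judgements. Schools and teachers cannot be masked here; the rater largely can be, and the plan makes no attempt to do so.

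An observer who knows that a school has received feedback has a reason to expect more activity there from that point on. A rating drift in that direction would look like an intervention effect. Collecting more lessons would not help, because a bias that runs one way within an arm does not average out. The interviews offer a concrete route to learning the arm: they concern the tool, they include the same teachers who are observed, and nothing prevents an interviewer from returning as an observer.

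**Working it through.** The plan gives no figure on this point (no power, SD or effect size), so there is nothing to reproduce. The check has four parts.

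**1. Do the existing safeguards withhold the arm?** The plan provides SOFIT training, a validated tool, audio pacing, headcount rules for start and stop, four-minute rotation, random observation days, no interaction during lessons, and absence of the study team from audit, feedback and technical-assistance meetings. The last of these separates the team from delivery of the intervention. The others standardize measurement or limit contact during lessons. None keeps the arm from the observer.

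**2. What survives a difference in change?** Let b(arm, period) be the mean rating bias. The bias in the estimated effect is

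[b(I, post) − b(I, pre)] − [b(C, post) − b(C, pre)].

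Illustrative values, with control bias 0 throughout:
- Constant at 5 points in the intervention arm: (5 − 5) − 0 = 0. It cancels.
- None in PY1, 5 points after feedback: (5 − 0) − 0 = 5 points. It remains in full.
- 3 points in PY1, growing to 5: (5 − 3) − 0 = 2 points. Only the growth remains.

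The same expression covers differences between observers. If each school keeps its observers throughout, their fixed differences cancel. If assignments change over time differently by arm, they do not, and the planned model has no observer term to absorb them.

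**3. When could interviews reveal the arm?** The interview paragraph first places interviews in PY2 and PY3. It then says that a person who takes part in both years is interviewed in PY1 and PY2, after the spring SOFIT observations. On the first reading with that spring timing, PY2 interviews precede the two PY3 semesters of observation. On the second, interviews start a year earlier. PY3 coding is open to this route on either reading.

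**4. Scale.** Lessons: 3 classes × 4 teachers × 10 schools × 6 semesters = 720, rising to 3 × 5 × 10 × 6 = 900 if every school has a PE teacher. Coding every 20 seconds gives 3 codes a minute, so an assumed 30-minute lesson has 90 codes and one code is worth 100/90 = 1.1 points (1.7 for 20 minutes, 0.8 for 40). At any lesson length, a net shift of 1 code in 20 across the MVPA boundary is 5 points and 1 in 10 is 10 points.

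To show what a residual bias would do, take a two-sided 5% t-test on school-level changes, 5 versus 5, no true effect: df = 8, noncentrality = bias / (SD × √(2/5)). For bias 5 and SD 5 this is 5 / (5 × 0.632) = 1.58. The SDs and biases are assumptions, and the t-test is a simplification of the planned mixed model.

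| Residual bias (points) | SD 5 | SD 8 | SD 10 |
|---|---|---|---|
| 0 | 5.0% | 5.0% | 5.0% |
| 2 | 8.7% | 6.4% | 5.9% |
| 3 | 13.4% | 8.2% | 7.0% |
| 5 | 28.6% | 14.1% | 10.8% |

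Entries are false-positive rates.

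**The case against.** The strongest reply is that the plan nowhere says observers know the arm, and that several links in the argument are permitted by the text without being stated in it. Four readings that a reader might infer go too far.

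- *That arm knowledge necessarily arrives after the PY1 baseline.* The study team itself randomizes the schools, and the audit takes place in spring PY1, so an observer could know the arm during PY1. A bias that was constant from then on would cancel.
- *That observer differences are confounded with treatment.* No passage suggests that observers are tied to one arm, and stable assignments would cancel in any case.
- *That observers choose the children at their discretion.* The selection is described as random and fixed at 2 girls and 2 boys. Only the mechanism is missing. The 51% start is likewise a headcount rule.
- *That the bias has a known size.* The 1-in-20 shift is arithmetic, and the table rests on assumed inputs.

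The scope is also limited. The study's objective is compliance with state PE law, MVPA is one of three listed outcomes, and none of the nine audit indicators names it.

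All of this stands, and it narrows the point. It does not remove it. Even an observer who knew the arm from PY1 would have little reason to expect improvement until feedback begins in fall PY2, so an expectation effect need not be constant. Pilot status lowers the stakes, but the plan does compare the arms on this outcome.

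**Conclusion.** The concern holds as a gap in conduct: the plan leaves the MVPA comparison open to observer expectation and does nothing to keep the arm from the people who rate. It should be corrected. It does not show that bias has occurred.

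The conclusion depends on two conditions that the documents neither establish nor exclude: that some observers learn the arm, and that any resulting bias appears or grows after feedback starts. Observer differences matter only if assignments shift over time differently by arm. The magnitude is unknown. Under the assumed SDs of 5 to 10 points, a residual bias of 3 points would raise a nominal 5% error rate to between 7.0% and 13.4%, and one of 5 points to between 10.8% and 28.6%. Scheduled minutes come from schedules and are unaffected; observed class length is less exposed because of the headcount rules.

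**What to change.** In the Study Protocol:
- State that SOFIT observers are not told the arm and receive only the school, teacher and class time.
- As far as existing staffing allows, let no one observe a school where they have already conducted interviews or read transcripts.
- Assign each observer to schools in both arms, in similar proportion, in every semester, and record observer ID for each lesson.
- Log any unmasking and report it as a limitation.
- As a minor point, use a pre-generated random list to carry out the planned selection of 2 girls and 2 boys.
- Reconcile the interview years (PY2 and PY3 against PY1 and PY2).

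In the Statistical Analysis Plan, add a sensitivity analysis of MVPA that includes observer in the model.

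If fieldwork is already complete, report who observed and who interviewed at each school, run the observer sensitivity analysis where IDs exist, and state that observers were not masked.

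The cost is mainly wording and task allocation. Visit scheduling becomes less flexible, and masking will be imperfect in a small team. Team size is not given, which is why the separation from interviewing is conditional on staffing.

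### The unpaired t-test of study schools against all district elementary schools counts the 10 study schools in both groups

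*Combined protocol and SAP*

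**What the plan says.** The Statistical Analysis Plan section, first paragraph, sets out two comparisons of school-level demographic data. The first concerns "Differences in school-level characteristics between all district elementary schools and study schools"; the second sets intervention schools against control schools. Both "will be determined using unpaired t-tests". The section does not say whether the pooled-variance or the Welch form is meant, and it gives no significance level.

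The Study Protocol section, first paragraph, shows where the study schools come from: "Our recent survey of all elementary school principals in REDACTED DISTRICT identified 15 elementary schools that are currently non-compliant" with state law, or unsure. The survey is to be repeated, the schools are to come "from the pool of schools with the lowest reported weekly PE minutes", and recruitment continues until the team has "our sample of 10 schools that are willing to participate". Every study school is therefore an elementary school of the district. Neither section takes the study schools out of the district group, and neither gives the number of elementary schools in the district.

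**The concern.** An unpaired t-test assumes that the two samples are independent. Here one sample is a subset of the other, so the two means are positively correlated and the test's standard error leaves that correlation out.

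At stake is the description of how far the study schools resemble the rest of the district. Real differences are plausible. The schools are chosen for low reported PE minutes, and the Study Protocol names enrollment and the share of low-income students as factors that hinder compliance. A test that is too insensitive could leave such differences unflagged.

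**Working it through.** **Inputs.** From the Study Protocol: n = 10 study schools, all in the district. Assumed, because the documents do not give them: N (30 to 500), a two-sided 5% level, the SDs, and the shape of the data. The plan states no figure for this comparison, so there is none to reproduce.

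**Covariance.** Let σ_s be the SD among study schools. The district mean is (10 × study mean + (N − 10) × mean of the rest)/N, so

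Cov(study mean, district mean) = (10/N) × σ_s²/10 = σ_s²/N.

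The unpaired test takes this as zero.

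**Estimate.** Study mean − district mean = ((N − 10)/N) × (study mean − mean of the rest). The difference reported is a shrunken version of the one of interest.

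**Standard error, equal SDs.** The test uses σ²(1/10 + 1/N); the true variance is σ²(1/10 − 1/N). The ratio of standard errors, used to true, is sqrt((N + 10)/(N − 10)). For N = 30 this is sqrt(40/20) = 1.414; for N = 100 it is sqrt(110/90) = 1.106. The shrinkage reduces the estimate and its true standard error by the same factor, so it costs no power by itself. Power is lost because the standard error in use is too large.

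**Size at nominal 5%.** Simulation with no true difference, equal SDs, normal data, 400,000 replicates per cell:

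| N | (N − 10)/N | SE used / true | Size, Welch | Size, pooled |
|---|---|---|---|---|
| 30 | 0.67 | 1.414 | 0.9% | 0.4% |
| 50 | 0.80 | 1.225 | 2.2% | 1.4% |
| 100 | 0.90 | 1.106 | 3.5% | 2.8% |
| 150 | 0.93 | 1.069 | 4.0% | 3.4% |
| 500 | 0.98 | 1.020 | 4.7% | 4.5% |

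Under the same assumptions, comparing the 10 schools with the other N − 10 gives 4.7% to 5.2% for pooled and 4.9% to 5.2% for Welch (N = 15 to 200).

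**Power.** True difference of 1 SD between study schools and the rest, equal SDs, normal data, Welch, overlapping v disjoint: about 0.35 v 0.68 at N = 30, 0.58 v 0.75 at N = 50, and 0.71 v 0.78 at N = 100.

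**Where the conditions fail.**

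- *Unequal SDs, pooled form, normal data.* With study schools 1.3 times as variable as the rest, the overlapping test rejects 3.0% at N = 50, 4.9% at N = 70, 5.7% at N = 80 and 6.8% at N = 100. It passes 5% at about N = 70 to 80. The disjoint pooled test at that ratio rejects 9.4% at N = 50 and 11.1% at N = 100. With a ratio of 0.75 and N = 100 the figures are 0.6% overlapping and 1.3% disjoint.
- *Skewed data.* With lognormal data (log-scale SD 0.8, same distribution in both groups) and N = 100, overlapping Welch rejects 8.6%, disjoint Welch 10.3% and disjoint pooled 5.1%.

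In each of these cases the overlap lowers the rejection rate relative to the disjoint version of the same test. The departures above 5% come from unequal variance, or from skewness with n = 10.

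**The case against.** **The wording may be shorthand for study schools against the rest.** That is possible, and nothing shows otherwise. But an analyst who follows the sentence literally would put the study schools in both groups, so the clarification is still needed.

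**The size depends on an unknown.** This stands. N is not given, and the effect fades to 2% of the standard error at N = 500. A reader might take the lowest value the text allows, N = 15, where the formula gives sqrt(25/5) = 2.236, and call the defect near-total. The documents do not support that reading. It would need every elementary school in the district to be non-compliant or unsure, whereas the survey is described as picking out 15 schools from all those surveyed.

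**Welch does not guarantee a conservative test.** This also stands. A reader might infer that the overlap makes a Welch test conservative whatever the data. The lognormal runs contradict that.

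**Requiring Welch is a separate matter.** A reader might also infer that removing the overlap is not enough and that Welch must be specified. That rests on an assumed SD ratio such as 1.3, for which the documents offer nothing; with equal SDs, removing the overlap restores the level for the pooled test too. On the lognormal data disjoint Welch rejects about twice as often as disjoint pooled.

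**Little depends on the comparison.** This is largely right. It is descriptive, in a 10-school pilot, with no decision rule attached. The schools are selected, not randomly sampled, so error rates are only a benchmark for how the test behaves.

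**Conclusion.** The plan is wrong as written: the two groups in this unpaired test share the 10 study schools, and independence fails. That conclusion needs no assumption beyond the text. Its size does: with equal SDs the standard error is too large by 41%, 22%, 11%, 7% and 2% at assumed N of 30, 50, 100, 150 and 500. The claim that the test is conservative and loses power holds for similar SDs and roughly normal data; outside those conditions the size can lie above or below 5%.

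A reader might extend the point to the trial's results. The documents do not support that. The intervention and control schools are disjoint, so their t-test is unaffected, and the mixed models for PE minutes and MVPA do not use the district group. Severity: minor.

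**What to change.** In the first comparison of the Statistical Analysis Plan, replace the word 'all' in the description of the district group with 'the remaining (non-study)'. If that was always the intention, the change only records it. The cost is a few words in one sentence and one filter in the code; the data source is already planned.

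Stating the pooled or Welch form is optional and should follow from the data. Welch protects against unequal SDs when the data are roughly normal, but can reject too often with strongly skewed data and 10 schools. Describing the difference without a test would also avoid the problem.

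### Schools are randomised 5 v 5, but random effects for school and grade, read as intercepts, give no school-level error term for the difference in change, so its standard error can be too small or too large

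*Combined protocol and SAP*

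**What the plan says.** The Study Protocol will "use block randomization to randomize schools to intervention (n=5) and control (n=5) arms" after stratification: "we will stratify schools by enrollment and proportion of low-income students enrolled".

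The Statistical Analysis Plan describes the outcome model in one sentence: "Linear mixed effects models with random effects for school and grade will be used to determine" within-group changes and the "difference in change between intervention and control schools in: scheduled minutes of physical education/week", estimated minutes per week, and the proportion of observed lesson time in MVPA. It does not say:

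- whether the random effects are intercepts or slopes, or whether grade is nested in school or crossed with it;
- how time is coded, or what one record is for each outcome;
- which degrees of freedom are used.

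No section names a school-by-time effect, a teacher effect, cluster-robust errors or a school-level analysis.

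The data could have several levels. Lessons are sampled each semester by "observing 3 PE classes of 2 randomly selected 2nd and 5th grade teachers (n=4 teachers) and the PE teacher", if there is one. For schedules, "researchers will obtain school-level PE master schedules, which contain PE times for all classes in the school", and consenting teachers' "individual classroom PE schedules" are collected as well. The protocol does not say whether the same teachers are observed from year to year. In its interview paragraph it treats participation in both years as possible, not assured.

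**The concern.** The school is the randomised unit, so the error for a comparison of change must include how much schools within an arm differ in their change. A school intercept and a grade intercept are constant over time and drop out of a within-school change. The standard error then comes from the pooled residual, as if all schools in an arm moved together apart from record noise.

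Two omissions pull in opposite directions:

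1. **No school-by-time term.** If schools change by different amounts, the standard error is too small. This is likely here, because the protocol leaves changes to each principal and the district through a school action plan. One example is a master schedule covering all grades, which would move all of a school's classes together. Re-drawing teachers between years acts in the same direction for lesson records.
2. **No teacher or classroom term.** If the same teachers or classrooms are followed, their stable differences cancel from the change but remain in the residual. The standard error is then too large.

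At stake are the interval and any p-value for the comparison of arms: false precision for MVPA by lesson, and possibly a hidden real change for classroom-level scheduled minutes.

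**Working it through.** The plan gives no alpha, variance or sample-size figure to reproduce. The 5% level is only a yardstick, and every variance below is an assumption.

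**Inputs from the protocol.** Five schools per arm. Four classroom teachers x 3 lessons x 2 semesters = 24 lessons per school-year, or 5 x 3 x 2 = 30 with a PE teacher.

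**Set-up.** PY1 v PY3, balanced data, fixed effects for arm, year and arm x year, and a z-test because no df method is stated. Let *n* be records per school-year, *s* the school-by-year variance and *e* the residual variance.

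- Correct variance of the difference in change = (2/5) x 2 x T/n, where T = ns + e.
- The intercept model uses P in place of T. P pools T (8 df) with the within-school-year mean square W (20(n − 1) df).
- Model SE / true SE = √(P/T). Approximate rejection rate under the null = 2[1 − Φ(1.96√(P/T))].

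**MVPA by lesson, n = 24.** Total variance 1, school 0.10, no teacher variance, so W = e = 0.90 − s. At s = 0.05:

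- T = 24 x 0.05 + 0.85 = 2.05
- P = (8 x 2.05 + 460 x 0.85)/468 = 0.8705
- ratio = √(0.8705/2.05) = 0.65, and rejection 20.2%.

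| s | T | P | SE ratio | Formula | Simulated |
|---|---|---|---|---|---|
| 0 | 0.90 | 0.900 | 1.00 | 5.0% | 5.2% |
| 0.02 | 1.36 | 0.888 | 0.81 | 11.3% | 11.1% |
| 0.05 | 2.05 | 0.871 | 0.65 | 20.2% | 20.4% |
| 0.10 | 3.20 | 0.841 | 0.51 | 31.5% | 31.3% |

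Simulated rates use 20,000 trials per case. With 30 lessons they are 4.7, 12.9, 23.4 and 36.0%. Nesting grade in school moves the 24-lesson rates by at most 0.7 points.

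**Adding a teacher share of 0.10** (24 lessons, s = 0 / 0.02 / 0.05 / 0.10):

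- same teachers: 4.0 / 10.5 / 20.1 / 31.6%
- half kept: 7.7 / 14.8 / 23.0 / 33.8% (8,000 trials per case)
- all re-drawn: 11.9 / 17.7 / 25.4 / 35.1%

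**Scheduled minutes, four classrooms followed.** Year-to-year variance 1, of which a fraction q is shared within school; stable classroom variance v. Then T = 4q + (1 − q) = 1 + 3q, W = (1 − q) + v, and P = (8T + 60W)/68. With v = 1:

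- q = 0: T = 1, P = (8 + 120)/68 = 1.88, ratio 1.37
- q = 0.25: T = W = 1.75, ratio 1.00 (break-even)
- q = 1: T = 4, P = (32 + 60)/68 = 1.35, ratio 0.58

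| q | Simulated, v = 0 | Simulated, v = 1 |
|---|---|---|
| 0 | 5.4% | 0.8% |
| 0.10 | 10.1% | 2.3% |
| 0.25 | 17.4% | 5.6% |
| 0.50 | 29.4% | 12.1% |
| 1 | 52.6% | 26.9% |

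**Estimated minutes.** No unit or derivation is given. If the same lesson data were averaged to four teacher-year records, the rates at s = 0 / 0.02 / 0.05 / 0.10 are 5.7 / 10.7 / 17.7 / 25.8% with no teacher variance. With a teacher share of 0.10 and the same teachers they are 1.3 / 4.7 / 9.9 / 17.8%.

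**One record per school-year.** The residual is then itself the school-by-year error. What remains is z in place of t: P(|t₈| > 1.96) = 8.6%.

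**Alternative.** A t-test on ten school-level changes (8 df, critical value 2.31) rejected in 4.5 to 5.6% of the 20,000-trial cases.

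**The case against.** **The plan is under-specified rather than wrong.** Random effects could include a school time slope. That reading is not excluded, and on it a sentence of clarification would settle the main point. But the text does not say so, and an analyst who fits the model in its ordinary form gets the wrong error term. Record unit and degrees of freedom would remain open either way.

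**With one record per school-year there is a school-level error term.** This is true, and master schedules make it possible for scheduled minutes. A random grade effect, however, implies more than one record per school-year.

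**The two directions are not equal.** This stands. For lesson data, over-caution is slight (4.0% against 5% at a teacher share of 0.10). It matters only for schedule or averaged records on the same teachers or classrooms. If half the classrooms are kept, with equal stable variance, the rates are 3.0% and 5.0% at 0 and 10% shared.

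**The variances are assumed and this is a pilot.** Both are true. The plan still sets out to determine the difference in change, and a misleading interval harms a pilot too.

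**The remedy was tested on balanced, complete data.** This also stands. A PE teacher in only some schools would make precision unequal, and no power was computed for the t-test.

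**Conclusion.** The concern holds, on the condition that the random effects are intercepts and there is more than one record per school-year. The plan should be changed before the data are analysed. It does not let a reader tell whether the interval for the comparison of arms is too narrow or too wide. For MVPA by lesson the main risk is too narrow: even a 2% school-by-year share about doubles the false-positive rate. For classroom-level scheduled minutes it can go either way, depending on whether classrooms are followed and how far a school's classes move together. The exact rates depend on assumed variances. That school and grade intercepts cancel from a change does not, and the 8-df comparison kept close to its level throughout.

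**What to change.** 1. **Specify.** For each of the three outcomes, state the record unit, time coding and follow-up year, the random-effects structure, and whether teachers or classrooms are followed. Say how a PE teacher's lessons enter the grade effect.
2. **Add a school-level comparison.** For each outcome, compute one change per school from PY1 to the stated follow-up, and compare 5 v 5 by t-test on 8 df, as the main analysis or a named check. If the strata predict change, the unadjusted test errs towards caution: with two assumed strata explaining 25 or 50% of the variance of school change, it rejected 3.9 or 3.0%. A stratum term suits few strata. Two leave 10 − 2 − 1 = 7 df (critical value 2.36); four leave 5 df (2.57).
3. **If the mixed model is kept** with several records per school-year, add a school-by-year (or random school time) effect and a teacher- or classroom-within-school effect, with small-sample df. Lessons can be linked to teachers: "The only identifiable information that will be collected will be the teacher name", with teacher type and sex.

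**Cost.** SAP wording and a few lines of code; no new data. The average school-level interval was 1.1 to 2.4 times as wide as the stated model's for 24-lesson outcomes. For four-classroom schedules it was 1.14 to 3.43 times as wide with no stable classroom variance, and 0.84 to 1.98 times with equal stable variance. Where the stated model over-rejects, the added width removes false precision. The extended mixed model on 8 df is cautious when schools differ little in change: it rejected 1.6 to 1.8% at a school-by-year share of 0, rising to 5.1 to 5.2% at 0.10.
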